Data at pre- and post-surveys will be collected on tablets using surveys programmed into REDCap. Computerized assessments are transferred electronically to UTHealth on a daily basis. We have used similar protocols with our previous homeless youth studies with success. REDCap is a well-tested computerized survey program. Our staff are trained in REDCap surveys, and our extensive experience should reduce implementation, data management, and design problems. Participants entering data will be able to interrupt and resume sections in mid-course, review previously entered data, and back up to change prior entries. The quality of the data on these programs is enhanced, as REDCap will provide immediate feedback to the participant if unexpected data are entered. Only data analysis personnel connected with the study will have access to data files. Those files will be de-identified and not contain any identifying information.

Paper Study Documents. To reduce the risk of transmission of infectious diseases, all documents will be programmed as forms in REDCap and accessible only to study staff. Paper documents will only be used as a back up and any collected hard copies will be saved in a secured and locked filing cabinet at the UTHealth Cizik School of Nursing for seven years. All study related forms, surveys, and data will be destroyed by shredding after seven years. In order to assure security of the data, we will make weekly backup copies of the REDCap data set. These copies will be stored in a secure area physically separate from the data management and analysis sections of the main project site.

Phone Data Loss Prevention. Participants will be provided with a study-issued smart phone to allow them access to pre-programmed homeless youth resources and the behavior feedback interface for the intervention arm. The phone will also be equipped with capability to conduct video phone calls in the event that the intervention needs to be delivered remotely. As well, the phones will facilitate tracking of participants, in addition to our extensive tracking protocol, to enhance follow-up retention. In our previous study, we had a phone loss or damage rate of 12%. If a phone is lost, it will be remotely wiped by UTHealth IT AirWatch system. No replacement phone will be provided to the participant in the event of a lost, stolen, or damaged phone. Paper versions of the daily diaries will also be available. No data will be collected or

stored on the phones. Phone lines will be disconnected after 12 months or when study staff determines that the phone is lost, stolen, non-functional, or no longer being used for study purposes.

Role of the PI and Investigative Team. [name] will have primary responsibility for monitoring study research staff, who will receive training on the study design, recruitment, and protocol prior to study initiation. Research staff will receive formal training on the study protocol by Drs. [name], [name], and [name], which will entail 2 weeks of intensive training session followed by additional training sessions as needed. The team will attend bi-weekly team meetings during data collection with the principal and co-investigators to discuss any study issues regarding recruitment and follow-up data collection and weekly meetings with [name]. These meetings will be used to discuss experiences with the intervention participants, provide consultation, ascertain whether the research staff are following study protocols, evaluate and reinforce cultural competence, and identify any potential adverse reactions. [name], study statistician, will coordinate data management and analysis. He will oversee development of data entry screens and the database development, supervise data entry verification, and work with the investigators in conducting all data analyses.

Drs. [name], [name], [name], [name], [name], and [name] will meet every other week (by phone and/or in person) to monitor study progress. Any adverse reactions noted by any of the team members will be immediately reported to the principal investigator, the UTHealth IRB, Data Safety and Monitoring Board, and NIH. One focus of investigator meetings will be on developing strategies to prevent adverse reactions and to better monitor the research staff and data integrity. Accrual data will be reviewed by the UTHealth IRB. The study team will make amendments to the protocol should accrual fall below 15% of the target, or should drop-outs exceed projections by 15%.

Quality control and assurance

Role of the Safety Monitoring Committee. The SMC is responsible for oversight of the activities related to implementing the clinical trial to ensure patient safety, conformance to the clinical protocol, overall performance of the trial components, and integrity of the data being collected. The SMC will meet prior to participant enrollment and then meet quarterly to review adverse events and participant safety concerns and annually to review study progress (e.g., recruitment retention, and safety procedures). Data quality and completeness and timeliness will be provided to the SMC including total number participants screened, enrollment rates, exclusion rates and reasons, randomization numbers, completion of scheduled follow-ups, reasons for study withdrawal, referral site rates, adequacy of enrollment composition, demographic similarities/differences between intervention and control group, protocol deviations and adherence, compromises in confidentiality. All meeting materials will be considered privileged by SMC members. This confidentiality should be maintained at all times to the extent permitted by law.

The SMC will comprise 3 members with expertise in risk prevention, health communication, and/or homeless youth intervention research. These members have extensive expertise to review the scientific design and conduct of a study, to evaluate safety and risks to participants, to interpret data statistically, and to make recommendations concerning continuation, modification, suspension, or termination of a study. [name], Social Work Scientist

at the University of Houston Graduate College of Social Work; [name], Anthropologist at the University of California San Francisco Center for AIDS Prevention Studies; and [name], Behavioral Scientist at the UTHealth School of Public Health will be the monitoring committee members (see Letters of Support).

SMC meetings conducted quarterly will begin after the first week of data collection. In addition, should any adverse event occur, the monitoring committee will be informed immediately, and a special session will be scheduled to discuss strategies to deal with the event. The quarterly meeting will include a synopsis of protocol and design, discussion of the status of interventions and data collection procedures, a summary of subject contacts, discussion of any adverse events or potential adverse events, status of data entry and verification, and a summary of any descriptive and inferential statistics to date. Data quality and completeness and timeliness will be provided to the SMC including total number participants screened, enrollment rates, exclusion rates and reasons, randomization numbers, completion of scheduled follow-ups, reasons for study withdrawal, referral site rates, adequacy of enrollment composition, demographic similarities/differences between intervention and control group, protocol deviations and adherence, compromises in confidentiality. The SMC will meet in a closed session without the investigators. In this meeting, the committee will discuss the need for additional procedures to prevent adverse events or ensure data integrity. In the unlikely case that the study may need an early termination due to unexpected adverse events or inadequate conduct of the study, the committee will make recommendations to the investigators. Recommendations from the monitoring committee meetings will be shared with the UTHealth IRB and NIH during annual reports and immediately if the monitoring committee identifies adverse events not previously reported or recommends early termination of the study.

Role of the IRB. This study will be approved by the UTHealth IRB. The UTHealth IRB will be the primary oversight IRB for the study and the study PI ([name]) will be responsible for reporting to the IRB about the status of the study. Annual progress reports and renewals will be completed for the IRBs and will include a summary of the recommendations of the monitoring committee. If adverse reactions related to study procedures are noted, they will be immediately reported to UTH IRB by [name] so that the IRB is aware of any risks involved with the study. The IRB will be responsible for ensuring adequate and appropriate membership composition of the SMC as specified by NINR policy.

Reporting to NINR. [name], the PI, will be responsible for submitting necessary reports to NINR. Summaries of the protocol and design, status of intervention group, data collection procedures, summary of subject contacts, discussion of any adverse reactions or any potential adverse reactions, status of data entry and verification, a summary of any descriptive statistics to date, and the recommendations of the monitoring committee will be included in each annual report to NINR. NINR will be notified within 7 days if the human subjects research or DSM plan is changed prior to or during implementation of the clinical trial for approval. In addition, should any adverse reaction occur or should the monitoring committee recommend early termination of the study, the information will be immediately reported to the NINR program officer. All personal identifiers will be removed from any documentation sent to NINR. Timely reports to NINR will be generated for:

- Unanticipated problems or unexpected serious adverse events that may be related to the study protocol
- IRB-approved revisions to the study protocol that indicate a change in risk for participants
- A summary of recommendations made by the SMC or other monitoring entity as appropriate and (if applicable) the action plan for response
- Notice of any actions taken by the IRB or regulatory bodies regarding the research and any responses to those actions

Publication Plan

Dissemination Plan

Drs. [name] (PI) and [name] at the University of Texas Health Science Center at Houston Cizik School of Nursing, Drs. [name] and [name] at the Baylor College of Medicine, [name] at the University of California San Francisco, and [name] at the University of California Irvine are committed to the timely dissemination of the research findings. [name] (PI) will ensure that this clinical trial will be registered on ClinicalTrials.gov (no later than 21 days after enrolling the first subject) and the updates (at least once every 12 months) and results (not later than one year after clinical trial completion date) are submitted to ClinicalTrials.gov according to the NIH Policy on the Dissemination of NIH-Funded Clinical Trial Information and in compliance with UTHealth policy requirements. Informed consent documents for the clinical trial will include a specific statement relating to posting of clinical trial information at ClinicalTrials.gov. [name] will be responsible for ensuring that the timelines are met according to the NIH Policy. [name] will also ensure that the informed consents at the University of Texas Health Science Center include a specific statement on the posting of clinical trial information to ClinicalTrials.gov and the protections afforded by the Certificate of Confidentiality. The University of Texas Health Science Center at Houston Committee for the Protection of Human Subjects has a policy posted on clinical trials registration and the reporting of the results are in compliance with NIH policy requirements.

During the first biannual meeting with the co-investigators, we will create a plan regarding the dissemination of the protocol and preliminary and final results of this clinical trial. Included in this list of abstracts and papers will be potential journals and conferences these results will be disseminated to, and when. We will also include in the list the potential first authors of these abstracts and papers. The data generated from this study will be presented at national or international conferences and indexed journals in a timely manner. We will submit all final peer-reviewed manuscripts from the data generated by this clinical trial to the digital archive PubMed Central.

Aggregated results in lay person terms will be shared with the participants, partnering agencies, and the larger community in addition to the scientific presentations and publications.

References

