Accomplishment of goals occur by addressing cognitive appraisals (clarifying misconceptions), promoting health seeking, and addressing knowledge and coping behaviors that incorporate the situational, personal, social, and resource needs affecting health. NCM involves coordinated, individualized, comprehensive care delivered by a registered nurse (RN) that includes a comprehensive health assessment, mutual care plan development, prevention education, and health and social service navigation.⁵²⁻⁵⁵ A nurse-led intervention eliminates the need to refer YEH to other medical professionals for HIV prevention services (e.g., PrEP, nPEP, lab draws, STI testing/treatment), a step that may increase compliance. This is particularly important as being homeless can decrease effectiveness of linkages to care⁵⁶ vs. providing care at the point-of-contact. NCM has been efficacious in reducing drug use among methadone users⁵⁷ and YEH,⁵⁴ improving hepatitis B vaccination rates,⁵⁸ reducing repeat pregnancies, and facilitating HIV care coordination.⁵⁹ NCM's comprehensive approach of simultaneously addressing concomitant problems (e.g., mental health, substance use, and housing needs) and incorporating the full continuum of behavioral and biomedical HIV prevention in an integrated fashion is a promising strategy for engaging YEH. Nurses are part of nearly all current HIV programs for YEH; therefore, our intervention is sustainable and can be easily integrated into existing HIV prevention programs.

We will strengthen NCM by integrating motivational interviewing (MI) and behavioral feedback. YEH are self-reliant, can be challenging to engage, and can become distrustful of adults due to past trauma and victimization on the streets.^{9,60} Therefore, we will integrate MI strategies into our NCM approach to strengthen the relationship between the YEH and RN and

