The YWG (n=10) will be currently or formerly YEH aged 16-25 years who will meet monthly in YR-1 then, if needed, to achieve the study aims and will be compensated at \$25 per working session. Lunch will be provided during the sessions. YWG members will assist in the development of study procedures, survey items, and recruitment materials to provide the experiential context of HIV risk. The RC and PI will co-chair YWG sessions and they will last 1-2 hours.

Intervention Description

Table 1. Differentiation between Usual Care and the NCM4HIV Intervention

| Current Usual Care Services Available | Expanded NCM4HIV Components |
|---|---|
| Housing, food, and clothing needs, health assessment, basic healthcare, limited anticipatory guidance, mental health counseling, substance use treatment referrals, PrEP/nPEP referrals | Personalized HIV prevention education, behavior goal-setting, behavioral self-monitoring, PrEP eligibility screening, PrEP/nPEP services (labs, medication), healthcare planning/coordination, MI counseling approach, assisting with cognitive appraisals (clarifying misconceptions), promoting health seeking and coping behaviors that incorporate the situational, personal, social, and resource needs affecting health |

An individual intervention design was chosen due to the heterogeneity of YEH and their risk behaviors and the challenges associated with group session designs including low attendance.¹⁰⁴

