The DSM plan is in accordance of the Policy of the National Institute of Nursing Research for Data and Safety Monitoring of Extramural Clinical Trials set forth in 2014. As part of the DSM plan, we have convened a Safety Monitoring Committee (SMC) of which the organization, responsibilities, and operation are mandated by NIH and NINR policy.

Trial Type/Level of Review. This study does not involve the testing of pharmacologic agents or any therapeutic treatments. Rather we are testing the efficacy of a nurse-led HIV prevention intervention. This study is classified as a Phase II of the Prevention Intervention Continuum – Methods Development, a minimal risk level study that dictates annual review by the IRB. To add additional safety measures for this study, we will convene a SMC. This study constitutes minimal psychological and physical risk and no legal or social risks. The risks are minimal since educational interventions generally promote good health, not endanger it. Our eligibility criteria are established to exclude individuals for whom the study procedures are not appropriate.

Monitoring Entity

Role of the PI and Investigative Team. [name] will have primary responsibility for monitoring study research staff, who will receive training on the study design, recruitment, and protocol prior to study initiation. Research staff will receive formal training on the study protocol by Drs. [name], [name], [name], and [name], which will entail 2 weeks of intensive training session followed by additional training sessions as needed. The team will attend bi-weekly team meetings during data collection with the principal and co-investigators to discuss any study issues regarding recruitment and follow-up data collection and weekly meetings with [name]. These meetings will be used to discuss experiences with the intervention participants, provide consultation, ascertain whether the research staff are following study protocols, evaluate and reinforce cultural competence, and identify any potential adverse reactions. [name], study statistician, will coordinate data management and analysis. He will oversee development of data entry screens and the database development, supervise data entry verification, and work with the investigators in conducting all data analyses.

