Reporting to NINR. [name], the PI, will be responsible for submitting necessary reports to NINR. Summaries of the protocol and design, status of intervention group, data collection procedures, summary of subject contacts, discussion of any adverse reactions or any potential adverse reactions, status of data entry and verification, a summary of any descriptive statistics to date, and the recommendations of the monitoring committee will be included in each annual report to NINR. NINR will be notified within 7 days if the human subjects research or DSM plan is changed prior to or during implementation of the clinical trial for approval. In addition, should any adverse reaction occur or should the monitoring committee recommend

early termination of the study, the information will be immediately reported to the NINR program officer. All personal identifiers will be removed from any documentation sent to NINR. Timely reports to NINR will be generated for:

- Unanticipated problems or unexpected serious adverse events that may be related to the study protocol
- IRB-approved revisions to the study protocol that indicate a change in risk for participants
- A summary of recommendations made by the SMC or other monitoring entity as appropriate and (if applicable) the action plan for response
- Notice of any actions taken by the IRB or regulatory bodies regarding the research and any responses to those actions

DSM Procedures

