Adverse Event Reporting. Study participants will be encouraged to immediately report any "emergencies or events" by calling the study contact number. These instructions will be included on all instructions that are sent to participants, programmed into the study issued cell phones, and on the consent forms. The study team will record all reported events in the adverse events and unanticipated problems log (including the subject's name, date, and event description). All members of the study team will inform the principal investigator, [name] [name] immediately, of any adverse events and unanticipated problems who will consult with co-investigators and the safety monitoring committee members on the action. The PI will report the incident to the UTHealth IRB within one week. The action and date of implementation will also be recorded in the adverse event unanticipated problems log. The entire investigative team and monitoring committee will participate in classifying events as "serious" or "non-serious" (see list below), as well as "non-attributable," "possibly attributable" or "attributable" to the intervention (unlike a pharmaceutical trial where known side effects exist, the classification of "expected" vs. "unexpected" is inappropriate for this behavioral intervention). The SMC will advise the PI and the study team on actions to be taken to minimize further adverse events and unanticipated problems within 2 weeks of reviewing the reports.

1. Serious events include any event or condition that is life threatening, results in a hospitalization, cancer or a physical or cardiac event serious enough to require medical attention. These events may be:
 - a. Fatal
 - b. Life threatening

- c. Permanently disabling
- d. Required or prolonged hospitalization (Admission—not ER visit)
- e. Overdose
- f. Significant hazard to patient

2. Non-Serious events includes all other events.

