A few potential minimal risks to subjects exist such as breach of confidentiality or normal risks associated with having a phone. Breach of confidentiality is not believed to present any significant risk given the data protections described above. However, to mitigate this risk we have outlined steps we will take to protect confidentiality in the Human Subjects sections, **Safeguarding Confidentiality and Certificate of Confidentiality**. Before data collection is initiated, researchers will obtain a Certificate of Confidentiality from NIH to protect participants from the requested release of study data. All participants will be informed that this certificate has been obtained, and what protections it affords them during the informed consent process. Participant data will not be released to any party outside the research team.

Potential Risks.

There are no physical risks associated with participation. The risk of psychological distress is related to the potential of receiving a positive HIV or STI test result. The types of study questions concerning past events, current circumstances, thoughts and feelings, sexual behaviors, substance use, and sexually transmitted infections may cause distress. Participants may find thinking about and answering questions about these issues upsetting; these questions will be asked in as sensitive a manner as possible. While participants will be assured that their participation will not affect health and social services being provided at any location, some participants may feel concerned about or pressured to be part of the study. Another potential risk is the loss of confidentiality or disclosure of information or data about the participant. While there were no reported adverse reactions to Nurse Case Management in our previous studies, there is the potential of stress and negative reactions from the self-reflection during the sessions.

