For data collection, participants may find thinking about thoughts and feelings that arise or answering questions about these issues upsetting; these questions will be asked in as sensitive a manner as possible. As well, if a participant answers no to a sexual activity question, they would not receive additional, more details questions about sex. By tailoring the questions, we minimize the exposure to sensitive questions and reduce the burden and fatigue that may arise from taking a survey. We use ACASI computer-based surveys to allow participants to read and answer the questions privately and not have to hear them aloud or tell another person, which may reduce any possible distress associated with answering the questions. While participants will be assured that their participation will not affect health and social services being provided at any location, some participants may feel concerned about or pressured to be part of the study. We will verbally assure participants at the beginning of each NCM session and at each follow-up that their participation is voluntary and that they can participate in all, part of, or none of the session and can withdraw from the study at any time for any reason without penalty. Another potential risk is the loss of confidentiality or disclosure of information or data about the participant. We have detailed below extensive measures to ensure confidentiality and decrease the risk for disclosure of private information.

During data collection, participants may refuse to answer any questions that make them feel uncomfortable. Participants may discontinue participation in the study at any time. We anticipate that the types of adverse experiences that may occur, if any, may be associated with issues

arising during data collection. None of these risks are considered significant. Having a study phone poses no more risk than having a personal phone.

This is a single site study.

Ongoing assessments that may impact safety or ethics of the study

The research team is active in HIV prevention research and will continue to monitor the literature, attend national and international conferences, and consult with colleagues to assure that we are aware of any emerging data that may impact safety or the ethics of the study.

Advanced plans for interim/futility analysis

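### The adverse-event classification and the risk statement treat NCM4HIV as purely behavioral, although it includes lab work, PrEP dispensing and nPEP starts (minor)

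*Combined protocol and SAP*

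**What the plan says.** Under Adverse Event Reporting, the investigators and the Safety Monitoring Committee (SMC) class each event as serious or not, and on a three-level scale of attribution to the intervention. A parenthetical beginning "unlike a pharmaceutical trial where known side effects exist, the classification of" goes on to call the expected/unexpected split unsuitable for a behavioral intervention.

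The Potential Risks section opens: "There are no physical risks associated with participation". It later anticipates that "the types of adverse experiences that may occur, if any, may be associated with issues" arising during data collection. Trial Type/Level of Review, in the data safety and monitoring plan, puts risk slightly differently: "This study constitutes minimal psychological and physical risk and no legal or social risks". Its reason is: "The risks are minimal since educational interventions generally promote good health, not endanger it".

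Reporting to NINR, which appears twice in the same words (in the monitoring plan and under Quality control and assurance), lists among its reporting triggers: "Unanticipated problems or unexpected serious adverse events that may be related to the study protocol".

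The intervention is described elsewhere. The Background says a nurse-led model removes the need to refer youth elsewhere for "HIV prevention services (e.g., PrEP, nPEP, lab draws, STI testing/treatment"). Table 1 of the Intervention Description lists "PrEP/nPEP services (labs, medication") among the components NCM4HIV adds; the usual-care column offers PrEP/nPEP referrals.

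**The concern.** The reason for dropping expectedness is that there are no known side effects to refer to. That would fit a counseling program. It does not fit one that supplies prescription medication and laboratory monitoring, and whose nurse explains the risks of PrEP to the participant.

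Three things are at stake, all in safety oversight. A known effect of PrEP and a surprising one would carry the same label. A reporting trigger that depends on the word unexpected has no procedure behind it. And because PrEP use is planned to differ sharply between arms, an excess of intervention-attributable events in the NCM4HIV arm could be ordinary drug effects or harm from the sessions, and the label would not say which. Sample size and efficacy estimates are not involved.

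**Working it through.** The point rests mainly on comparing sections. Arithmetic enters only to show the scale of exposure.

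**1. Is the premise true of this intervention?** Under HIV Risk Profile and PrEP Eligibility Assessment, the nurse discusses the risks and benefits of PrEP with eligible youth. If the participant is interested, the nurse begins lab work that includes kidney function, and then dispenses PrEP at the session. After a recent sexual assault, nPEP is started with consent if the participant is inside the 72-hour window. Table 1 counts labs and medication as intervention components. Events from them are therefore events of the intervention, and their risks are risks of participation. The premise fails, and so does the statement of no physical risk.

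**2. Does the NINR trigger have a classification step?** Reporting to NINR needs a serious event to be judged unexpected. Adverse Event Reporting is the only section that defines event classes, and it excludes that one. In the available text, no section assigns expectedness, against one trigger (stated twice) that requires it.

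**3. Do the risk statements agree?** Trial Type/Level of Review says minimal physical risk; Potential Risks says none. The difference is small, but the second cannot stand beside step 1. The reason given for minimal risk, that the intervention is educational, does not cover medication or blood draws.

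**4. Planned exposure.** Inputs: 300 intervention and 150 control (Randomization); PrEP uptake moving from 2% to 24% and from 2% to 4% respectively (Sample Size and Power Calculations); 210 and 105 retained at 9 months (same section).
- As randomized: 0.24 × 300 = 72 against 0.04 × 150 = 6.
- New starts, assuming the 2% already on PrEP continue: (0.24 − 0.02) × 300 = 66 against (0.04 − 0.02) × 150 = 3.
- Among those retained: 0.24 × 210 ≈ 50 against 0.04 × 105 ≈ 4.

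These are prescriptions, since uptake is verified from charts (Measures), not doses taken. The plan does not say how many youth would have lab work. If every new starter does, the intervention-arm figure lies between 66 and a ceiling of 0.84 × 300 = 252, using the plan's 84% eligibility. The ceiling would need every eligible youth to be interested.

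**5. Can drug and session events be separated with what is collected?** Partly. Chart-verified prescriptions (Measures) show who was prescribed the drug. Session notes (Intervention Fidelity Checks and Study Staff Training) and the details of serious health events recorded at follow-up (DSM Procedures) give context. But exposure is not attribution: an event in a PrEP user may still come from the sessions. The recorded judgment is a single attribution to the intervention as a whole.

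**The case against.** The best defense is that nothing is lost. Any adverse reaction goes immediately to NINR (Reporting to NINR) and to the IRB, SMC and NINR (the paragraphs under Role of NIH; see also Role of the IRB). That largely covers the narrower trigger, and without an expectedness label the default is to report more, which is the safe direction. This stands. A reader might infer that unexpected serious events could go unreported; the documents do not support that.

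Second, the plan says correctly that no pharmacologic agent is under test, and PrEP follows clinical guidelines and standing orders under physician supervision. This also stands, but it concerns clinical care and regulatory status. Events are attributed to the intervention, and risks are stated for participation; medication belongs to both whether or not it is investigational.

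Third, the existing records help separate causes. It would be too strong to say that only the free-text event description could do so. The full log is not in the documents either: the three items named are given as inclusions, so unlisted fields may exist.

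Fourth, the plan does give some account of what is anticipated. Potential Risks covers distress from test results and questions, loss of confidentiality, and negative reactions to self-reflection in the sessions, and the data-collection sentence is not worded as exclusive. So it would be wrong to say that no anticipated risks are listed. The list is incomplete: it omits medication and lab procedures.

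Finally, the exposure figures come with no adverse-event rate, so no number of misclassified events can be derived. That is correct, and none is claimed.

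**Conclusion.** The point holds as a minor defect in event classification and in the protocol's risk statement. The parenthetical against expectedness and the claim of no physical risk are both wrong for an intervention that supplies PrEP/nPEP labs and medication. The first leaves the NINR trigger on unexpected serious events without a classification step; the second disagrees with the monitoring plan's own wording.

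The practical size is limited. PrEP uptake of about 72 of 300 against 6 of 150 rests on the plan's power assumptions and full arm sizes, and shows how uneven drug exposure would be. It says nothing about how many events would occur. The consequence is a safety comparison between arms that is harder to interpret than it need be, partly recoverable from prescriptions, session notes and event details.

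A reader might also infer that participants were not told of medication risks. The consent pages are not available, and the plan has the nurse discuss PrEP risks with eligible youth, so no such conclusion is drawn.

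**What to change.** - In Adverse Event Reporting, delete the parenthetical. For PrEP/nPEP and lab-procedure events, class expectedness against the product labeling. A written reference would also support consistent decisions by a committee made up of a social work scientist, an anthropologist and a behavioral scientist, even with study physicians available.
- On the event form, record attribution to medication or labs separately from attribution to the sessions.
- In Potential Risks, replace the statement of no physical risks with the medication and blood-draw risks, worded to agree with the minimal-risk statement in Trial Type/Level of Review. Add medication and lab events to the anticipated adverse experiences.

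Reporting timelines, clinical PrEP/nPEP rules, sample size and efficacy analyses stay as they are. The cost is a few sentences and two form fields. The downside is slightly more classification work and a less reassuring risk statement.
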